10.1 Primary Objectives

10.1.1 To evaluate the negative predictive value (NPV) of post-treatment FLT PET/CT imaging for complete remission (CR) in patients receiving induction chemotherapy for acute myeloid leukemia (AML).

Three imaging parameters (SUV_{mean}, SUV_{max}, SUV_{hetero}) will be measured from an FLT PET/CT scan, and SUV_{max} will be the primary endpoint. The binomial proportion of NPV and the corresponding Exact confidence intervals will be calculated. In addition, the calculated NPV will be tested against the null hypothesis to see if it's significantly larger than 0.64 (NPV of Day-14 BMBX in CR prediction).

Rev. 10/16

10.2 Secondary Objectives

10.2.1 *To evaluate the positive predictive value (PPV) of post-treatment FLT PET/CT imaging for complete remission;*

The binomial proportion of PPV and the corresponding Exact confidence intervals will be calculated. In addition, the calculated PPV will be tested to see if it's significantly larger than 0.79 (PPV of Day-14 BMBX in CR prediction).

Rev. 10/16

Rev. 10/16

Rev. Add3

10.2.2 *To estimate the sensitivity and specificity of post-treatment FLT PET/CT for detecting complete remission;*
The binomial proportions and the corresponding Exact confidence intervals will be calculated for sensitivity and specificity estimation.

10.2.3 To correlate FLT PET/CT imaging parameters with biologic correlates (MRD assessment).
Correlation and regression analysis will be used to assess this aim.

10.2.4 To correlate FLT PET/CT imaging parameters with relapse-free survival and overall survival.
Kaplan-Meier method and Cox proportional hazard regression will be used to assess this aim

10.3 **Exploratory Objectives**

10.3.1 *To evaluate pre-treatment FLT PET/CT activity as a predictor of complete remission;*
No previous studies were available to determine the cutoff for the pre-treatment SUV_{max}. The ROC approach will be used to test the continuous measurement of this variable in predicting CR.

10.3.2 *To evaluate the change between pre-treatment and post-treatment FLT PET/CT activity as a predictor of complete remission;*
No previous studies were available to determine the cutoff for the change from pre-treatment to post-treatment SUV_{max}. The ROC approach will be used to test the continuous measurement of this variable in predicting CR.

Safety Monitoring

Interim analyses of toxicity are performed twice yearly for all ECOG-ACRIN studies. Reports of these analyses are sent to the ECOG-ACRIN Principal Investigator or Senior Investigator at the participating institutions. Expedited reporting of certain adverse events is required, as described in Section [Error! Reference source not found.](#)

Rev. Add3

10.4 Gender and Ethnicity

Based on previous data from E1900 the anticipated accrual in subgroups defined by gender and race is:

Racial Categories	Ethnic Categories				Total	
	Hispanic or Latino		Not Hispanic or Latino			
	Females	Males	Females	Males		
American Indian or Alaskan Native	0	0	0	0	0	
Asian	0	0	2	0	2	
Native Hawaiian or other Pacific Islander	0	0	0	0	0	
Black or African American	0	0	3	2	5	
White	4	3	35	34	76	
Total	4	3	40	36	83	

The accrual targets in individual cells are not large enough for definitive subgroup analyses. Therefore, overall accrual to the study will not be extended to meet individual subgroup accrual targets.

Study Monitoring

This study will be monitored by the ECOG-ACRIN Data Safety Monitoring Committee (DSMC). The DSMC meets twice each year. For each meeting, all monitored studies are reviewed for safety and progress toward completion. When appropriate, the DSMC will also review interim analyses of outcome data. Copies of the toxicity reports prepared for the DSMC meetings are included in the study reports prepared for the ECOG-ACRIN group meeting (except that for double blind studies, the DSMC may review unblinded toxicity data, while only pooled or blinded data will be made public). These group meeting reports are made available to the local investigators, who may provide them to their IRBs. Only the study statistician and the DSMC members will have access to interim analyses of outcome data. Prior to completion of this study, any use of outcome data will require approval of the DSMC. Any DSMC recommendations for changes to this study will be circulated to the local investigators in the form of addenda to this protocol document. A complete copy of the ECOG-ACRIN DSMC Policy can be obtained from the ECOG-ACRIN Coordinating Center.

Evaluation of Toxicity

All subjects will be evaluable for toxicity from the time of injection of FLT until 24 hours after injection.

Evaluation of Preliminary Efficacy

A futility analysis will be performed when half of the participants (i.e., 34) have completed the trial. The method of conditional power [7] will be used for the futility analysis, which will estimate the probability that NPV with all subjects would be greater than 0.64, conditional on the results accumulated at the time of the futility analysis. If this probability is too small (i.e., < 0.20), implying that it is

Rev. Add3

unlikely that the FLT PET/CT is useful, then a decision may be made to terminate the study early.

Rev. 10/16 **11. Research Sample Submissions**

Bone marrow aspirates and/or peripheral blood must be submitted for defined laboratory research studies being performed at the ECOG-ACRIN LTRL. These laboratory research studies are defined in Section [12](#).

Bone marrow smears are to be submitted for future undefined research per patient consent.

It is **required** that all samples submitted on this trial be entered and tracked using the ECOG-ACRIN Sample Tracking System (STS) (see Section [11.3](#)). An STS shipping manifest form is to be included with every submission.

All samples must be labeled clearly with the ECOG-ACRIN protocol number (EAI141), ECOG-ACRIN patient sequence number, patient's initials, date of collection and sample type.

11.1 Sample Collection and Submission Schedule

Samples are to be submitted as follows:

11.1.1 Bone marrow and/or peripheral blood are to be submitted to the ECOG-ACRIN LTRL as outlined in Section [11.2](#). Samples are to be collected at the following time points:

Bone marrow aspirates (or peripheral blood) and bone marrow smears:

- Pre-Treatment

Bone marrow aspirates and bone marrow smears:

- Day 28-35 (Remission)

11.2 Submissions to ECOG-ACRIN Leukemia Translational Research Laboratory (LTRL)

[name] institutional regulations require that she receive a copy of the patient's consent and a copy of the HIPAA authorization at the time of or prior to the submission of the bone marrow samples.

11.2.1 Sample Preparation Guidelines

NOTE: FOR MRD ASSESSMENTS, AN ASPIRATE FROM A SEPARATE BONE MARROW ASPIRATION SITE MUST BE SUBMITTED (THE NEEDLE CAN BE REDIRECTED THROUGH THE SAME SKIN PUNCTURE SITE). ONLY SUBMIT ASPIRATES FROM THE FIRST PULL OF AN ASPIRATION SITE FOR MRD TESTING. DO NOT SUBMIT SAMPLES FROM THE SECOND OR THIRD PULL OF THE SAME ASPIRATION SITE.

NOTE: Results of MRD assessments will not be reported to the site.

The following are to be submitted:

1. **MANDATORY:** Heparinized bone marrow aspirate (the laboratory will accept any amount as long as it represents a first pull). Ideally,

2-3mL of aspirate from a separate aspiration site should be submitted.

For patients with an inaspirable bone marrow ("dry tap"), or if a bone marrow has been done previously and the patient refuses to have another aspiration done, call [name] laboratory at [contact] to discuss the case and the possibility for submitting peripheral blood only. Be prepared to report the WBC count and the blast count in the peripheral blood at the time of the call.

ALTERNATIVE TO BONE MARROW ASPIRATE SUBMISSION AT BASELINE: Heparin or EDTA peripheral blood (four [4] green or purple top tubes, 30-40mL).

NOTE: Peripheral blood must be submitted only if bone marrow aspirates will not be submitted at preregistration and can be submitted after registration to Step 1 to coincide with clinical assessments.

2. At least two (2) Wright-Giemsa stained bone marrow smears. Submit from patients who answer "Yes" to "I agree to provide additional samples for research."
3. **MANDATORY:** A copy of the institutional pathology report on the bone marrow must be submitted. The pathology report must include cytogenetic results and any results from fluorescence-in-situ (FISH) hybridization and/or molecular studies done at the submitting institution.

Please fax to the LTRL at [contact]

11.2.2 Shipping Procedures

The LTRL must be notified by telephone the day of shipment.

Fax or Email to [name] is not acceptable.

[contact]

During off hours, all information regarding the shipment should be left on the answering machine in the LTSI including:

EAI141 patient sequence number

Patient Initials

Type of specimens shipped

Name, telephone number, and institution

For questions regarding the shipment, [name] and her staff can be reached at the phone numbers provided on the recorded message, please always try [name] first. Questions can also be addressed to [name] via e-mail ([contact]), however, please do not use e-mail for the notification of shipments.

Bone marrow smears should be submitted within one week of collection.

Heparinized bone marrow aspirate and peripheral blood or EDTA samples must be sent fresh (on the day of collection) on cool packs

(do not freeze and do not use ice cubes) by overnight courier (preferably FedEx) to arrive within 24 hours to:

[name].
Department of Oncology
[name]
Leukemia Oncology Laboratory
[name]
[name]
[contact]
[contact]

The LTRL is open to receive shipments Monday through Saturday. Shipments on Fridays for Saturday delivery must have "Saturday Delivery" marked on the overnight courier slip.

In general, always ship specimens the day before a holiday for delivery the day after the holiday.

An STS shipping manifest form must be generated and shipped with all sample submissions.

Please enter all information into the STS, including time and date of specimen collection and peripheral blood WBC count and blast count.

If samples need to be drawn late at night, on Sunday, or on a holiday when FedEx does not operate, keep the samples in a refrigerator between 10 and 15 degrees Celsius until the next day when it can be shipped.

11.3 ECOG-ACRIN Sample Tracking System

It is **required** that all specimens submitted on this trial be entered and tracked using the ECOG-ACRIN Sample Tracking System (STS). The software will allow the use of either 1) an ECOG-ACRIN user-name and password previously assigned (for those already using STS), or 2) a CTSU username and password.

When you are ready to log the collection and/or shipment of the specimens required for this study, please access the Sample Tracking System software by clicking <https://webapps.ecog.org/Tst>.

Important: Please note that the STS software creates pop-up windows, so you will need to enable pop-ups within your web browser while using the software. A user manual and interactive demo are available by clicking this link:
<http://www.ecog.org/general/stsinfo.html>

Please take a moment to familiarize yourself with the software prior to using the system.

An STS generated shipping manifest form should be shipped with all specimen submissions.

Please direct your questions or comments pertaining to the STS to [contact].

11.3.1 Study Specific Notes

Generic Specimen Submission Form (#2981) will be required only if STS is unavailable at time of sample submission. Notify the laboratory of the shipment by faxing a copy of the completed form to the laboratory. Indicate the appropriate laboratory on the submission form:

- ECOG-ACRIN Leukemia Translational Research Laboratory

Retroactively, enter all specimen collection and shipping information when STS is available.

11.4 Use of Specimens in Research

Specimens from patients who consented to allow their specimens to be used for future ECOG-ACRIN approved research studies will be retained in the ECOG-ACRIN Leukemia Tissue Bank (LTB).

Specimens submitted will be processed to maximize their utility for current and future research projects.

If future use is denied or withdrawn by the patient, the specimens will be removed from consideration for use in any future research study.

11.5 Sample Inventory Submission Guidelines

Inventories of all samples submitted from institutions will be tracked via the ECOG-ACRIN STS and receipt and usability verified by the receiving laboratory. Inventories of samples forwarded by the LTRL/LTB and utilized for approved laboratory research studies will be submitted by the LTRL/LTB to the ECOG-ACRIN Operations Office – Boston on a monthly basis in an electronic format.

12. Leukemia Correlative Studies

12.1 Immunophenotype and Molecular Genetics

Immunophenotyping has become an essential part of the diagnostic work-up of all leukemia patients. In fact, the diagnosis of leukemia without immunophenotypic characterization is no longer acceptable. ECOG-ACRIN has, therefore, developed a model system for antigenic data collection that requests specimens from all patients entered on ECOG-ACRIN leukemia trials be studied by the ECOG-ACRIN LTRL. In addition to establishing the leukemia subtype, this centralized testing and data collection has allowed research questions of clinical relevance to be applied to a growing database (e.g., definition of prognostically significant antigen expression levels to eventually yield specific treatment subcategories). In EAI141, an additional significance for central immunophenotyping is provided by the flow cytometric assessment of minimal residual disease (MRD). Sample submissions for MRD determination in bone marrow aspirates will coincide with clinically required bone marrow examinations. The LTRL will use multiparameter 6-color flow cytometry of bone marrow aspirates using leukemia-associated immunophenotypes to detect residual blast cells.

Bone marrow from patients entered on studies of hematologic malignancies are stored in ECOG-ACRIN's LTB for EAI141 embedded and future laboratory studies. The bank provides the scientific community with a source of leukemia specimens that are collected, processed, and maintained following quality control and quality assurance guidelines. The bank will accommodate requests from investigators within and outside ECOG-ACRIN in a timely and efficient manner, with respect to tissue type, tissue preparation, and most importantly, biologic characteristics of specimens.

Appendix I

Patient Thank You Letter

We ask that the physician use the template contained in this appendix to prepare a letter thanking the patient for enrolling in this trial. The template is intended as a guide and can be downloaded from the web site at <http://www.ecog-acrin.org>. As this is a personal letter, physicians may elect to further tailor the text to their situation.

This small gesture is a part of a broader program being undertaken by ECOG-ACRIN and the NCI to increase awareness of the importance of clinical trials and improve accrual and follow-through. We appreciate your help in this effort.

[PATIENT NAME]

[DATE]

[PATIENT ADDRESS]

Dear [PATIENT SALUTATION],

Thank you for agreeing to take part in this important research study. Many questions remain unanswered in cancer. With the help of people like you who participate in clinical trials, we will achieve our goal of effectively treating and ultimately curing cancer.

We believe you will receive high quality, complete care. I and my research staff will maintain very close contact with you. This will allow me to provide you with the best care while learning as much as possible to help you and other patients.

On behalf of **[INSTITUTION]** and ECOG-ACRIN, we thank you again and look forward to helping you.

Sincerely,

[PHYSICIAN NAME]

Early Assessment of Treatment Response in AML using FLT PET/CT Imaging

Appendix II

EAI141 Adverse Event Reporting Guidance Document

Below are scenarios that a site may be faced with when assessing patients prior to and after the Day 14 FLT scan on EAI141. The below scenarios are to provide guidance on how to handle reporting on these issues. This is not an exhaustive list; if there is a situation you are unclear on for reporting please contact the Study Team.

When assessing patients prior to the Day 14 scan, ensure you document the patient was physically and mentally able to undergo the Day 14 scan.

Scenario #1

A subject develops grade 3 febrile neutropenia on hospital day 10 after the beginning of therapy. The grade 3 febrile neutropenia persists despite antibiotics through day 17. FLT is administered and imaging performed on day 14.

Does febrile neutropenia need to be reported as an SAE? No, the SAE is not a new event that occurred after FLT was given. If a fever is documented during the hospitalization prior to the scan, the day 15 fever should not be considered a new AE, therefore no reporting will occur.

Scenario #2

A subject develops grade 3 anemia (hemoglobin < 8 requiring transfusion) on hospital day 7. The patient requires transfusions every 2-3 days through day 20. FLT is administered and imaging performed on day 14. The anemia never becomes life-threatening (grade 4).

Does anemia need to be reported as an SAE? No, anemia was present prior to FLT administration and it has not changed in severity.

Scenario #3

A subject develops grade 3 mucositis. This occurs on day 15, and is attributed to chemotherapy. FLT was administered and imaging conducted on day 14.

Does this need to be reported as an SAE? Yes, though mucositis is not attributed to FLT but instead to chemotherapy, it occurred within the 24 hour monitoring period and must be reported within 24 hours via the AERS.

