5.4.5 Mechanisms for Adverse Event Reporting

Within the monitoring period:

- **Routine Reporting (RAVE)**
 - **All adverse events** (Grades 1-5) both serious and non-serious *worsening or emergent after IND administration/intervention*, within the monitoring period, regardless of hospitalization or attribution, must be reported using the routine reporting system.
- **Expedited Reporting (CTEP-AERS)**
 - **All serious adverse events** (Grades 1 and 2) *worsening or emergent after IND administration/intervention*, within the monitoring period, and *resulting in hospitalization or prolongation of hospitalization for 24 hours or more*, regardless of attribution, must be entered by the site using expedited reporting.
 - **All serious adverse events** (Grades 3, 4 and 5) *worsening or emergent after IND administration/intervention*, within the monitoring period, *regardless of hospitalization or attribution*, must be entered by the site using expedited reporting.

After the monitoring period:

- **Routine Reporting (RAVE)**
 - All adverse events, regardless of grade and attribution, that are reported through the expedited reporting system also must be reported using the routine reporting system.
 - **All Deaths** (Grade 5) While a patient is on-study, without exception, deaths must be entered via routine reporting.
- **Expedited Reporting (CTEP-AERS)**
 - All serious grade 2 events, resulting in hospitalization or prolongation of hospitalization for 24 hours or more, and having *an attribution of possible, probable, or definite*, must be entered by the site using expedited reporting.
 - All serious adverse events (Grades 3-5) having *an attribution of possible, probable, or definite*, must be entered by the site using expedited reporting.

- All Deaths (Grade 5) on-study, regardless of attribution, must be entered by the site using expedited reporting if it is within 30 days of IND agent administration/intervention. After the 30 day period and through the one year follow-up, only routine reporting is required.

AE monitoring period for F-18 (¹⁸F-FLT) PET IND:

The AE monitoring period for ¹⁸F-FLT, an ¹⁸F based radioisotope imaging agent with a half-life (t $\frac{1}{2}$ of 110 minutes and a 10 half-life equivalent of 18.33 hours) is 24 hours after administration of the IND.

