³As with many intravenously administered agents, 3'-deoxy-3'-[F-18]fluorothymidine could cause an allergic reaction that could potentially pose a threat to life (anaphylaxis). This has not been observed in limited human exposure to date. Reasonable precautions should be taken, consistent with normal radiologic and clinical facility practice. The patient should be monitored until the PET procedure is completed, and trained personnel and emergency equipment should be available per facility standards.

For purposes of informed consent regarding reasonably foreseeable risks to subjects in trials utilizing 3'-deoxy-3'-[F-18]fluorothymidine, the following potential adverse events are considered extremely rare:

[figure not shown]
- Injection-related risks that may include infection, or accidental extravasation of the dose that may lead to discomfort, localized pain, or infection.
- Risks related to allergic reaction/anaphylaxis that may be life threatening.

NOTE: As with all PET imaging agents, 3'-deoxy-3'-[F-18]fluorothymidine is a radiopharmaceutical that decays with positron emission. As such, it poses an intrinsic radiation exposure risk. However, when administered in accordance with the Investigator's Brochure as a PET imaging agent, this risk is felt to be extremely small. The organ and total body doses associated with FLT PET imaging are comparable to or lower than those associated with other widely used clinical nuclear medicine procedures.

NOTE: 3'-deoxy-3'-[F-18]fluorothymidine in combination with other agents could cause an exacerbation of any adverse event currently known to be caused by the other agent, or the combination may result in events never previously associated with either agent.

Rev. 7/17

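### The last sentence of Appendix II Scenario 1 is broader than its worked case and, read literally, excludes recurrent or worsened fever that section 5.4.5 makes reportable

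*Combined protocol and SAP*

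**What the plan says.** Section 5.4.5 sets the reporting test. Within the monitoring period, adverse events of every grade that are "worsening or emergent after IND administration/intervention" go into routine reporting in Rave. Serious grade 3 to 5 events meeting the same test also go into expedited reporting, whatever their attribution. The general AE definition in section 5.4.2 and the definition for IND imaging agents in section 5.4.5 use equivalent tests. Section 5.4.2 adds that an event starting before the reporting period counts as medical history or baseline. The monitoring period for FLT is 24 hours.

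Section 5.4.6 refers sites to Appendix II. In Scenario 1 the febrile neutropenia begins on day 10, FLT is given on day 14, and "The grade 3 febrile neutropenia persists despite antibiotics through day 17". Asked whether this must be reported as an SAE, the appendix answers: "No, the SAE is not a new event that occurred after FLT was given". It then adds: "If a fever is documented during the hospitalization prior to the scan, the day 15 fever should not be considered a new AE", from which it concludes that no reporting takes place.

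Scenario 2 asks the same question about anemia and answers: "No, anemia was present prior to FLT administration and it has not changed in severity".

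**The concern.** The added sentence replaces the test in section 5.4.5 with a different one. Section 5.4.5 asks whether the event appeared or got worse after FLT. The Scenario 1 sentence asks only whether some fever was recorded earlier in the same hospital stay. The two questions can have different answers for the same patient.

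What is at stake is the completeness of the FLT safety record. Section 5.5 states that no adverse events have been reported in human studies of the agent and that its table will be updated as the toxicity profile is revised. The foreseeable risks it lists include "Injection-related risks that may include infection, or accidental extravasation of the dose" and allergic reaction. That a fever could be an early sign of either is a clinical inference; section 5.5 does not name fever. Even so, section 5.4.5 captures events in the window regardless of presumed cause, so a likely origin in the disease or the chemotherapy is not a reason to leave a new fever out.

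**Working it through.** **Is a day 15 fever inside the monitoring period?** The inputs are the 110-minute half-life in section 5.4.5 and the rule there of 10 half-lives rounded up to a whole day.

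- 10 × 110 min = 1,100 min.
- 1,100 / 60 = 18.33 h, which matches the plan's figure.
- Rounded up to a whole day, this is 24 h, which also matches.

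A day 14 injection therefore has a window that runs to the same clock time on day 15. Scenario 3 confirms this: mucositis on day 15 after a day 14 scan is treated as inside the window and reportable, although it is attributed to chemotherapy.

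**Does the sentence go beyond the worked patient?** Its wording suggests that it does.

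- It is conditional on a fever having been documented. The Scenario 1 patient is already stated to be continuously ill from day 10 through day 17, so the condition adds nothing for that patient.
- The question asked was about an SAE, and the preceding sentence had already answered it. This sentence moves to AEs and to reporting in general, so it also reaches routine entry in Rave.

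**The two texts side by side, for fever within 24 hours after FLT:**

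| Case | Sections 5.4.2 and 5.4.5 | Scenario 1 sentence, read literally | Result |
|---|---|---|---|
| (a) Ongoing at injection, same grade afterwards | Baseline event, not worsened: not reported | Not reported | Agree |
| (b) Earlier fever resolved before injection, then returns | Emergent: reported | Not reported | Conflict |
| (c) Ongoing at injection, then rises in grade | Worsening: reported | Not reported | Conflict |
| (d) No earlier fever in the hospitalization | Emergent: reported | Condition not met, so section 5.4.5 governs | Agree |

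The baseline note in section 5.4.2 settles case (a). It does not settle (b), because the new episode begins inside the reporting period. Nor does it settle (c), because the AE definition in the same section includes conditions that worsen.

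**What would be left out in (b) and (c)?** Routine reporting at any grade would be omitted. For a serious grade 3 to 5 event, so would the expedited report, which section 5.4.5 requires initially within 24 hours and in complete form within 5 calendar days after that.

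**The case against.** The strongest reply is that the sentence belongs to a worked example. It speaks of one particular day 15 fever in a patient whose grade 3 febrile neutropenia never stopped, and the sentence before it gives the governing reason, that the event was not new after FLT. On those facts the answer agrees with section 5.4.5 and with the baseline note in section 5.4.2. Scenario 2, directly below, shows that unchanged severity is the intended test. The appendix calls itself guidance, says its list is not exhaustive and sends unclear situations to the study team. Section 5.4.5 separately lists rash, breathing difficulty, blood pressure instability and other allergic-type symptoms, and Scenario 1 removes none of these.

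Much of this stands. The worked answer is right, and the defect is confined to one loosely worded sentence. But the route to the study team helps only a site that finds the matter unclear, and this sentence gives a plain answer. A site should not have to borrow a condition from Scenario 2 that Scenario 1 leaves out.

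Two stronger readings are tempting, and the documents support neither. A reader might infer that the sentence switches off fever reporting for most of the cohort. The documents give no fever rate. The number of patients with any earlier fever would also be the wrong count, because patients whose fever continues unchanged are rightly not reported and those with no fever after FLT have nothing to report. A reader might also infer that post-injection fevers have been hidden. Nothing in the documents shows an omitted report; omission is only a possible effect of the wording.

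**Conclusion.** The point holds as a wording conflict with a definite but limited reach. Followed literally, the last sentence of Scenario 1 gives a result contrary to section 5.4.5 in cases (b) and (c) and in no other case examined. This rests on reading the sentence as the general condition that its grammar states, and not as a remark about one patient.

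Its size in patients is unknown. It depends on how many have a fever that recurs or rises in grade within 24 hours of FLT, and the documents give nothing from which to estimate that number; it may be small. Any omission would lower the recorded count of adverse events after FLT, but only that direction can be stated. Section 10 sets no hypothesis on a toxicity rate, and neither the primary NPV analysis nor the sample size is affected. The sentence should still be corrected, because sites are referred to this appendix and the remedy is short.

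**What to change.** Reconcile the sentence with section 5.4.5 by giving it the condition that Scenario 2 already carries. For example: a fever that belongs to an episode still ongoing at FLT injection, and that is not higher in grade during the following 24 hours, is not a new AE; a fever that had resolved before injection and returns within those 24 hours, or that rises in grade within them, is reported under section 5.4.5. The study team should also say what counts as resolved when fever is intermittent, or the new wording will carry its own ambiguity. Optionally, the presence and grade of fever just before injection could be recorded on the PET Adverse Event Assessment, which sites already submit after each scan.

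The cost is one sentence of appendix text and some additional reports. The attribution field will not screen these out: inside the monitoring period, serious grade 3 to 5 events need expedited reporting regardless of attribution, so some recurrent fevers due to the disease or its treatment will generate expedited reports.
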